Appendix F	N/A	
AMERICAN SOCIETY OF ANESTHESIOLOGISTS PHYSICAL STATUS CLASSIFICATION
 
 
 ASA PS 1	Normal healthy patient	
 
 ASA PS 2	Patients with mild systemic disease	
 
 ASA PS 3	Patients with severe systemic disease	
 
 ASA PS 4	Patients with severe systemic disease that is a constant threat to life	
 
 ASA PS 5	Moribund patients who are not expected to survive without the operation	
 
 ASA PS 6	A declared brain-dead patient whose organs are being removed for donor purposes	
 
 
ASA = American Society of Anesthesiology; PS = Physical Status
	ASA PS 1	Normal healthy patient	ASA PS 2	Patients with mild systemic disease	ASA PS 3	Patients with severe systemic disease	ASA PS 4	Patients with severe systemic disease that is a constant threat to life	ASA PS 5	Moribund patients who are not expected to survive without the operation	ASA PS 6	A declared brain-dead patient whose organs are being removed for donor purposes	Added to note ASA classifications.	NS
ASA PS 1	Normal healthy patient															
ASA PS 2	Patients with mild systemic disease															
ASA PS 3	Patients with severe systemic disease															
ASA PS 4	Patients with severe systemic disease that is a constant threat to life															
ASA PS 5	Moribund patients who are not expected to survive without the operation															
ASA PS 6	A declared brain-dead patient whose organs are being removed for donor purposes															
Appendix G	N/A	displayed	Added to summarize changes from the original protocol.	NS												

Synopsis Dosing table (original):

Dose	Timing of Last Dose of FXa Inhibitor	Initial IV Bolus		Follow-on IV Infusion
Low Dose	
≥ 8 hours
 
OR
 
< 8 hours for
 
 • Rivaroxaban \leq 10 mg • Apixaban \leq 5 mg • Enoxaparin \leq 40 mg 	400 mg at a target rate of 30 mg/min	4 mg/min for at least 120 minutes irrespective of the duration of surgery (extended infusion for longer surgeries)	
High Dose	
< 8 hours
 
 • Rivaroxaban > 10 mg; • Apixaban > 5 mg • Enoxaparin > 40 mg • Edoxaban 60 mg 
OR
 
Dose or Time Unknown
	800 mg at a target rate of 30 mg/min	8 mg/min for at least 120 minutes irrespective of the duration of surgery (extended infusion for longer surgeries)	Extended infusion (beyond 120 minutes) may be administered at 4 mg/min (low-dose) for up to 4 additional hours*

Synopsis Dosing Table (revised):

Andexanet Dose	Timing of Last Dose of FXa Inhibitor	Initial IV Bolus Dose		Follow-on IV-Extended Infusion
		Initial IV Bolus	Initial Follow-on IV Infusion	
Low Dose	
≥ 8 hours OR < 8 hours for
 
 • Rivaroxaban \leq10 mg • Apixaban \leq5 mg • Enoxaparin \leq40 mg • Edoxaban 30 mg 	400 mg at a target rate of 30 mg/min	4 mg/min for at least 120 minutes irrespective of the duration of surgery (extended infusion for longer surgeries)	
High Dose	
< 8 hours
 
 • Rivaroxaban > 10 mg; • Apixaban > 5 mg • Enoxaparin > 40 mg • Edoxaban 60 mg 
OR
 
> 15 hours or unknown time
 
 • Local anti-fXa > 100 ng/mL (0.5 IU/mL for enoxaparin) 
Dose or Time Unknown
	800 mg at a target rate of 30 mg/min	8 mg/min for at least 120 minutes irrespective of the duration of surgery (extended infusion for longer surgeries)	Extended infusion (beyond 120 minutes) may be administered at 4 mg/min (low-dose) for up to 4 additional hours*

SOA (original):

STUDY DAY:	Screening & Baseline		Treatment						Follow-Up		
	1		2				3		30 or ET		
TIME POINT AND WINDOW: All time points relative to start of surgery	-2 hours to -45 min	-45 min to -30 min	-30 min to -5 min	Start of Surgery (SoS) [1]	SoS + 1 h ± 15 min	SoS + 2 h ± 15 min	EoS [2] ± 15 min	SoS + 12 h ± 1 h	SoS + 24 h ± 1 h	SoS + 72 h ± 1 h	+ 7 days
Obtain Consent	X										
Determine Eligibility	X										
Obtain Medical History	X										
Obtain Prior Medications and Time of Last Anticoagulant Dose or Plasma Level	X										
Obtain ASA Class			X								
Vital Signs (BP, HR, RR, temp)	X	X		X	X	X	X	X			
Weight (actual reported/recent)	X										
Physical Examination	X								X	X	X
Central Labs: Anti-fXa and anti-IIa Activity		X			X		X	X			
Central Labs: Thrombin Generation	X	X			X		X	X	X	X	

STUDY DAY:	Screening & Baseline		Treatment						Follow-Up		
	-2 hours to -45 min	-45 min to -30 min	-30 min to -5 min	Start of Surgery (SoS) [1]	SoS + 1 h ± 15 min	SoS + 2 h ± 15 min	EoS [2] ± 15 min	SoS + 12 h ± 1 h	SoS + 24 h ± 1 h	SoS + 72 h ± 1 h	30 or ET
TIME POINT AND WINDOW: All time points relative to start of surgery	-2 hours to -45 min	-45 min to -30 min	-30 min to -5 min	1							
Central Labs: Antibodies to andexanet, HCPs, and FX/FXa (modified Bethesda); and nAb (andexanet)	X										X
Central Labs: TFPI activity		X					X	X	X	X	X
Local Labs: PT-INR	X										
Local Labs: Chemistry and Pregnancy Test [3]	X										
Local Labs: CBC		X					X	X			X
Prepare andexanet (all patients)	X										
Administer andexanet Bolus, Immediately Followed by an Infusion				Bolus + Infusion							
Assess Need for Extended Andexanet Infusion.(if Surgery Ongoing)						X [4]					
Surgical Intervention				SURGERY							
Record Blood Loss Post Surgery							X				
Record Investigator Assessment of Intra-operative Hemostasis							X				

STUDY DAY:	Screening & Baseline		Treatment						Follow-Up		
			1						2	3	30 or ET
TIME POINT AND WINDOW:	-2 hours to -45 min	-45 min to -30 min	-30 min to -5 min	Start of Surgery (SoS) [1]	SoS + 1 h ± 15 min	SoS + 2 h ± 15 min	EoS [2] ± 15 min	SoS + 12 h ± 1 h	SoS + 24 h ± 1 h	SoS + 72 h ± 1 h	+ 7 days
All time points relative to start of surgery											
Record Blood Products & Hemostatic Treatments [5]					X						
Record Bleeding-Related Diagnostic & Therapeutic Procedures [6]					X				X	X	
Record Volume of Colloid and Crystalloid [5]					X						
Record Hours in ED, ICU/Critical Care, General Hospital Floor, and Total as an Inpatient											X
Record AEs	X				X				X	X	X
Record Concomitant Medications	X				X				X	X	X
Ascertain Survival Status											X

AE = Adverse event; ASA = American Society of Anesthesiologists; BP = Blood pressure; CBC = Complete blood count; CRF = Case report form; CT = Computed tomography; d = Day(s); ED = Emergency department; EoS = End of Surgery; ET = Early Termination; FX = Factor X; FXa = Activated factor X; h = Hour(s); HCP = Host cell protein; HR = Heart rate; ICU = Intensive care unit; INR = International normalized ratio; IV = Intravenous; min = Minute(s); nAb = Neutralizing antibody (activity); PT = Prothrombin time; RR = Respiratory rate; SoS = Start of Surgery; Temp = Temperature; TFPI = Tissue factor pathway inhibitor

¹ Start of surgery is Time 0 and must be within 15 hours of the last FXa inhibitor dose.

² The EoS time point may occur before SoS + 1 hour or SoS + 2 hour; EoS procedures should be carried out when EoS occurs.

³ Pregnancy test in women of childbearing potential; test may be done on urine or serum.

⁴ Approximately 30-45 minutes prior to the end of the andexanet infusion, the investigator should inform the pharmacy whether additional andexanet will be needed, to allow time for preparation.

⁵ Colloid, crystalloid, hemostatic agents, and blood products administered prior to arrival in the ED should also be recorded.

⁶ Record procedures performed to evaluate bleeding source/extent and for treatment of bleeding.

SOA (revised):

STUDY DAY:	Screening & Baseline			Treatment				Follow-Up		
				1				2	3	30 or ET
TIME POINT AND WINDOW: All time points relative to start of surgery	-2 hours to -45 min	-45 min to -30 min	-30 min to -5 min	SeS + 1 h End of Bolus ± 15 min	SeS + 2 h ± EoII -15 min	EoS [2I] ± 15 min /2J	SeS EoS + 12 h ± 1 h	SeS EoS + 24 h ± 1 h	SeS EoS + 72 h ± 1 h	+ 7 days
Obtain Consent	X									
Determine Eligibility	X									
Obtain Medical History	X									
Demographics	X									
Obtain Prior Medications and Time of Last Anticoagulant Dose or Plasma Level	X									
Obtain ASA Class			X							
Vital Signs (BP, HR, RR, temp)	X	X		X	X	X	X	X	X	X
Weight (actual reported/recent)	X									X
Physical Examination	X						X	X	X	X
Central Labs: Anti-fXa and anti-IIa Activity		X (pre-ADX)		X	X	X	X	X		
Central Labs: Thrombin Generation	X	X (pre-ADX)		X	X	X	X	X	X	X
Central Labs: Antibodies to andexanet, HCPs, and FX/FXa (modified Bethesda); and nAb (andexanet)		X (pre-ADX)								X
Central Labs: TFPI activity		X (pre-ADX)		X	X	X	X	X	X	X
Local Labs: PT-INR	X									
Local Labs: Chemistry and Pregnancy Test [3]	X									

STUDY DAY:	Screening & Baseline		Treatment					Follow-Up			
			1						2	3	30 or ET
TIME POINT AND WINDOW: All time points relative to start of surgery	-2 hours to -45 min	-45 min to -30 min	-30 min to -5 min	SoS + 1 h End of Bolus ± 15 min	SoS + 2 h ± EoII -15 min	EoS [2I] ± 15 min [2I]	SoS EoS + 12 h ± 1 h	SoS EoS + 24 h ± 1 h	SoS EoS + 72 h ± 1 h		+ 7 days
Local Labs: CBC		X				X	X	X		X	
Prepare Andexanet (all patients)	X										
Administer Andexanet Bolus, Immediately Followed by an Infusion			Bolus + Infusion X								
Assess Need for Extended Andexanet Infusion.(if Surgery Ongoing)					X [4]						
Surgical Intervention				SURGERY							
Record Blood Loss Post Surgery						X					
Record Investigator Assessment of Intra-operative Intraoperative Hemostasis						X					
Record Blood Products & Hemostatic Treatments [5]				X							
Record Bleeding-Related Diagnostic & Therapeutic Procedures [6]				X					X	X	
Record Volume of Colloid and Crystalloid [5]				X							
Record Hours in ED, PACU , ICU/Critical Care, General Hospital Floor, and Total as an Inpatient										X	
Record AEs	X			X					X	X	
Record Concomitant Medications	X			X					X	X	

STUDY DAY:	Screening & Baseline		Treatment					Follow-Up		
	1	2	3	30 or ET						
TIME POINT AND WINDOW: All time points relative to start of surgery	-2 hours to -45 min	-45 min to -30 min	-30 min to -5 min	SoS + 1 h End of Bolus ± 15 min	SoS + 2 h ± EoII -15 min	EoS [2I] ± 15 min [2J]	SoS EoS + 12 h ± 1 h	SoS EoS + 24 h ± 1 h	SoS EoS + 72 h ± 1 h	+ 7 days
Ascertain Survival Status										X

AE = Adverse event; ASA = American Society of Anesthesiologists; BP = Blood pressure; CBC = Complete blood count; CRF = Case report form; CT = Computed tomography; d = Day(s); ED = Emergency department; *EoII = End of Initial Infusion*; EoS = End of Surgery; ET = Early Termination; FX = Factor X; FXa = Activated factor X; h = Hour(s); HCP = Host cell protein; HR = Heart rate; ICU = Intensive care unit; INR = International normalized ratio; IV = Intravenous; min = Minute(s); nAb = Neutralizing antibody (activity); *OR = operating room; PACU = Post-anesthesia care unit; PT = Prothrombin time; RR = Respiratory rate; SoS = Start of Surgery; Temp = Temperature; TFPI = Tissue factor pathway inhibitor*

¹ Start of surgery is Time 0 and must be within 15 hours of the last FXa inhibitor dose. *The EoS time point before may occur SoS + 1 hour or SoS + 2 hour; EoS procedures should be carried out when EoS occurs.*

² The EoS time point may occur before SoS + 1 hour or SoS + 2 hour; EoS procedures should be carried out when EoS occurs. *Collect EoS samples within 15 minutes from the end of surgery but before stopping infusion.*

³ Pregnancy test in women of childbearing potential; test may be done on urine or serum.

⁴ Approximately 30-45 minutes prior to the end of the andexanet infusion, the investigator should inform the pharmacy whether additional andexanet will be needed, to allow time for preparation.

⁵ Colloid, crystalloid, hemostatic agents, and blood products administered prior to arrival in the ED should also be recorded.

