10.1.5. Anticoagulant Dose or Plasma Level

Patients will be asked about the brand, dose and time of last dose of their anticoagulant. For patients who received the last dose of FXa inhibitor more than 15 hours (or an unknown time) prior to start of surgery, a local anti-fXa activity level may be obtained to allow enrollment of patients with >100 ng/mL levels. See Section [10.2.1](#) below on details for this local testing.

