10.2.1. Anti-fXa Activity

Anti-fXa activity will be measured using plasma samples to assess the ability of andexanet to reverse the anticoagulant effect of FXa inhibitors. Anti-fXa activity will be measured by a modified chromogenic assay. These assays will be performed at a Central Laboratory.

Local laboratory anti-fXa activity testing may be utilized additionally by sites to ascertain eligibility (>100 ng/ml) if the time of last dose of FXa inhibitor is greater than 15 hours (or unknown). Local laboratory testing post-andexanet administration should be done with caution due to potential invalidity of local lab results from excessive sample dilution.

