Synopsis, Inclusion Criteria	
All of the following criteria must be met for the patient to be eligible:
 
 1. Either the patient or their medical proxy (or legal designee) has given written informed consent. 2. Age \geq 18 and $<$ 85. 3. Requires urgent surgical intervention that 	
All of the following criteria must be met for the patient to be eligible:
 
 1. Either the patient or their medical proxy (or legal designee) has given written informed consent. 2. Age \geq 18 and < 85 years old. 3. Requires urgent surgical intervention that 	
Added assessment for anti-FXa activity level.
 
Added clarification on
	S

	
must occur within 12 hours of clinical presentation, for which reversal of anti-fXa activity is judged necessary.
 
4. Received 1 of the following FXa inhibitors within 15 hours prior to start of surgery: apixaban, rivaroxaban, edoxaban, or enoxaparin (dose of enoxaparin ≥ 1 mg/kg/d), OR if a local anti-fXa activity level obtained within 2 hours prior to consent is > 100 ng/mL (> 0.5 IU/mL for enoxaparin), the patient may be enrolled, irrespective of the time of the last dose.
 
5. Have a negative pregnancy test documented prior to enrollment (for women of childbearing potential).
 
6. Willingness to use medically acceptable methods of contraception through 30 days following study drug dose (for female and male patients who are fertile).
	
must occur within 12 hours of clinical presentation consent, for which reversal of anti-fXa activity is judged necessary.
 
4. Received 1 of the following FXa inhibitors within 15 hours prior to start of surgery: apixaban, rivaroxaban, edoxaban, or enoxaparin (dose of enoxaparin ≥ 1 mg/kg/d), OR if, within 15 hours prior to start of surgery. If the time from the last dose is unknown or greater than 15 hours, the patient may be enrolled provided a local laboratory anti-fXa activity level obtained within 2 hours prior to consent is > 100 ng/mL (> 0.5 IU/mL for enoxaparin), the patient may be enrolled, irrespective of the time of the last dose.
 
5. Have a negative pregnancy test documented prior to enrollment (for women of childbearing potential).
 
6. Willingness to use medically acceptable methods of contraception through 30 days following study drug dose (for female and male patients who are fertile).
	multiple inclusion criteria.	

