3.4.1 Study Population	
The study will enroll patients between the ages of 18 and 85 who have recently taken an FXa inhibitor (i.e., within 15 hours prior to surgery or if a local anti-fXa activity level obtained within 2 hours prior to consent is > 100 ng/mL [> 0.5 IU/mL for enoxaparin]) and who require urgent surgery for which reversal of anti-fXa activity is judged necessary.
 
Only patients who are in need of surgery that, in the opinion of the Investigator, cannot be delayed by 12 hours are to be enrolled. Procedures that are associated with a low bleeding risk are not eligible.
	
The study will enroll patients between the ages of 18 and 85 years who have recently taken an FXa inhibitor (i.e., within 15 hours prior to start of surgery or if a local anti-fXa activity level obtained within 2 hours prior to consent is > 100 ng/mL [> 0.5 IU/mL for enoxaparin]) and who require urgent surgery for which reversal of anti-fXa activity is judged necessary.
 
Only patients If the time from last dose is unknown or greater than 15 hours, the patient may be enrolled provided a local anti-fXa activity level obtained within 2 hours prior to consent is > 100 ng/mL [> 0.5 IU/mL for enoxaparin]. In such cases the start of surgery must be no greater than 4
	Language added to more accurately detail potential risks.	S

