6.2. Dosing and Administration

The initial andexanet dosing regimen will consist of an IV bolus, immediately followed by an IV continuous infusion lasting for 2 hours, irrespective of the duration of surgery. The start of the bolus will occur prior to, but not more than 30 minutes before, the start of surgery (i.e., at the first incision). It is possible that the bolus or infusion may be ongoing at the start of surgery. There are 2 possible dosing regimens ([Table 2](#)).

If the initial andexanet dosing regimen (bolus plus continuous infusion; ~2.5 hours) is completed prior to the end of the procedure, the infusion should continue at a low dose (4 mg/min) through the end of the surgery and the immediate post-operative period. To facilitate the extended infusion, approximately 30 minutes prior to the end of the andexanet infusion, the investigator should inform the pharmacy whether additional andexanet will be needed, to allow time for preparation. The total length of the initial course of andexanet (initial bolus/infusion plus extended infusion) should last no longer than 6 hours.

If a post-operative patient meets the applicable criteria for andexanet re-dosing (Table 2), he/she may be re-dosed. All patients that are re-dosed will be administered a low-dose bolus (400 mg) plus continuous infusion (4 mg/min for 120 minutes). If a patient is re-dosed, a baseline anti-fXa activity sample will be drawn beforehand; no post-initiation anti-fXa activity will be obtained.

Table 2: Andexanet Dosing Paradigm and Criteria for Extended Treatment or Re-Dosing

Dose	Timing of Last Dose of FXa Inhibitor	Initial IV Bolus *	Follow-On IV Infusion *
Low Dose	≥ 8 hours OR < 8 hours for 
 • Rivaroxaban \leq 10 mg • Apixaban \leq 5 mg • Enoxaparin \leq 40 mg 	400 mg at a target rate of 30 mg/min	4 mg/min for at least 120 minutes irrespective of the duration of surgery (extended treatment for longer surgeries)
High Dose	< 8 hours 
 • Rivaroxaban > 10 mg; • Apixaban > 5 mg • Enoxaparin > 40 mg • Edoxaban 60 mg OR Dose or Time Unknown	800 mg at a target rate of 30 mg/min	8 mg/min for at least 120 minutes irrespective of the duration of surgery (extended treatment for longer surgeries)
Criteria for Re-Dosing with Andexanet			
Consider re-dosing with andexanet (400 mg bolus + 4 mg/min infusion) only if:			

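### The revised dosing table printed in Appendix G puts eligible patients with a known last dose more than 15 hours earlier in both the Low Dose and High Dose rows (880 mg versus 1,760 mg), with no stated precedence

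*Protocol*

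**What the plan says.** The relevant text is in the protocol's Appendix G, under the revised synopsis dosing table.

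- **Low Dose row.** The timing condition is "≥ 8 hours OR < 8 hours for" a list of lower inhibitor doses. There is no upper time limit.
- **High Dose row.** Besides the list for doses taken under 8 hours earlier, Amendment 1 adds a line for more than "15 hours or unknown time", qualified by "Local anti-fXa > 100 ng/mL (0.5 IU/mL for enoxaparin").
- **Eligibility.** The new text of inclusion criterion 4 in Appendix G reads "If the time from the last dose is unknown or greater than 15 hours, the patient may be enrolled provided a local laboratory anti-fXa" level exceeds those same thresholds. The new text for Section 3.4.1 repeats the rule.
- **Current body text.** Amendment 1 keeps this route into the study. Section 10.1.5 says that for a last dose "more than 15 hours (or an unknown time) prior to start of surgery, a local anti-fXa activity level may be obtained" to allow enrolment, and Section 10.2.1 agrees.
- **Original protocol.** In Section 6.2, Table 2, the only High Dose entry beyond the under-8-hour list was "Dose or Time Unknown". A known dose at a known time beyond 15 hours therefore matched Low Dose alone.

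**The concern.** The amendment gave patients beyond 15 hours their own High Dose line but did not take them out of the Low Dose row. The local level that triggers the High Dose line is also the condition for enrolling them, so the overlap covers the whole group with a known time beyond 15 hours.

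A site that stops reading at the 8-hour condition would give half the initial dose that the added line indicates. These patients were enrolled because their measured anti-fXa activity was still above the threshold. The mistake is easy to make, because the unbounded row is the one that applied to this group in the original Table 2. Dose also matters in the other direction: Section 1.4.6 of the original protocol describes dose-dependent increases in coagulation markers, and thrombotic events are the adverse events of special interest. The row should not depend on which line is read first, shortly before urgent surgery.

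**Working it through.** **Regimen totals.** The inputs are the bolus doses, the 30 mg/min bolus rate and the infusion rates over 120 minutes, all from the revised table. The total is bolus + rate × 120.

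- Bolus time: 400/30 = 13.3 min and 800/30 = 26.7 min. These agree with the stated durations of about 15 and up to 30 minutes in Section 3.4.2 of the original protocol.
- Length of the high regimen: (26.7 + 120)/60 = 2.44 h, in line with the stated figure of about 2.5 hours.
- Low: 400 + 4 × 120 = 880 mg.
- High: 800 + 8 × 120 = 1,760 mg.
- Difference 880 mg; ratio 1,760/880 = 2.0.

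A full 4-hour extension runs at 4 mg/min in either regimen and adds 4 × 240 = 960 mg to each (1,840 versus 2,720 mg). The difference stays at 880 mg.

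**Row logic.** Each timing category is read against the two rows as printed, with a qualifying local level present.

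| Time since last dose | Low Dose row met | High Dose row met |
|---|---|---|
| 5 h, listed lower inhibitor dose | yes | no |
| 5 h, higher inhibitor dose | no | yes |
| 8, 12 or 15 h | yes | no |
| 15.1 or 20 h | yes | yes |
| unknown | no | yes |

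Only a known time beyond 15 hours meets both rows, and it does so whatever the inhibitor dose.

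**Is there a tie-breaker?** None was found in the available text. The new Section 5.2 text in Appendix G bases the dose on product, inhibitor dose and time of last dose; it does not mention the local level that triggers the High Dose line. The original Section 3.4.2 gives a PK-PD rationale for stepping down at 8 hours, with no upper limit. That favours Low Dose, whereas the added line favours High Dose.

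**Could lost formatting explain it?** Strikethrough is lost in this copy. However, deleted words survive in it, as the superseded unknown-dose-or-time entry does beside its replacement. An inserted upper limit should therefore also be visible. If the 8-hour condition itself had been struck, patients at 8 to 15 hours would have no dose at all.

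**The case against.** The strongest objection is about the source. The table stands in a summary of changes. The available Amendment 1 text starts in Section 9, so its synopsis and Section 6.2 Table 2 cannot be checked, and those are the texts a site would be expected to dose from. The table in Appendix G is also an imperfect witness: the version labelled as original carries an extended-infusion cell that neither the original synopsis table nor the original Table 2 contains. This objection stands and limits the point to the table as printed. It does not remove the point, because the conflict is between two rows of the same revised table, not between the log and current text.

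Second, a specific line with a laboratory qualifier is ordinarily read as overriding a general one; otherwise the added words on more than 15 hours would do nothing for a known time. The original table already needed such a reading, since a known time of 8 hours or more with an unknown dose met both of its rows. This also stands. It shows which row is probably meant, but the table does not say so.

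Third, capping Low Dose at 15 hours would open a gap. A patient enrolled within 15 hours without a local test, whose incision slips past 15 hours, would have no row. The new text makes that patient ineligible without the local level, but an exception clause is still safer than a cap.

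A reader might go further and infer that the operative dosing instructions contradict themselves, that patients were given the wrong dose, or that Low Dose is inadequate beyond 15 hours. The documents support none of these. The operative tables are not available, no dosing data are given, and the stated rationale for the 8-hour step-down argues against assuming inadequacy.

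**Conclusion.** The point holds in a limited form. As printed in Appendix G, the revised table assigns eligible patients with a known last dose more than 15 hours earlier to both rows, with a two-fold difference in the initial regimen and no stated precedence. High Dose is probably intended. Patients with an unknown time, or a known time up to 15 hours, are not affected by this overlap.

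The conclusion assumes that the printed cells are faithful on this point. Whether it reaches practice depends on whether the operative Amendment 1 tables carry the same wording, which cannot be settled here. The size of the affected group is not stated. It would be wrong to infer a bias in the hemostasis or anti-fXa results: nothing available shows that any patient's dose was affected. This is a minor dosing-safety correction, worth making because it costs almost nothing.

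**What to change.** In the Low Dose timing cell, write: *≥ 8 hours (except patients > 15 hours enrolled on a qualifying local anti-fXa level: see High Dose)*. Keep the list for doses under 8 hours and the added High Dose line as they are. A known time beyond 15 hours with a qualifying level then meets High Dose only, 8 to 15 hours stays Low Dose, and a patient whose surgery slips past 15 hours without a local test still has a row.

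The sponsor should check the operative Amendment 1 synopsis table and Section 6.2 Table 2 and make the same change there if they carry this wording. The cost is one line of table text and, if those tables are affected, a short clarification to sites. It needs no additional patients, procedures or data fields.
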